- 10) Subject has a condition(s) that may interfere with the TKA or UKA survival or outcome (i.e., Paget's or Charcot's disease, vascular insufficiency, muscular atrophy, uncontrolled diabetes, moderate to severe renal insufficiency or neuromuscular disease, or an active, local infection).
- 11) Subject in the opinion of the Investigator has an emotional or neurological condition that would pre-empt their ability or willingness to participate in the study including mental illness, mental retardation, drug or alcohol abuse.
- 12) Subject, in the opinion of the Investigator, has a neuromuscular disorder that prohibited control of the index joint
- 13) Subject is a prisoner or meets the definition of a Vulnerable Subject per ISO 14155 Section 3.55.

Study Duration: Estimated total study timeline: 36 months (Enrolment period: 24 months, Follow-up period: 12 months)

Primary endpoint: The evaluation of the proportion of subjects achieving post-operative leg alignment at 6 weeks post-surgery. Achieved leg alignment is defined as $\pm 3^\circ$ from the subject's specific target.

Secondary endpoint(s):

- Component Alignment 6 weeks post-surgery
- Radiographic assessment (Presence of radiolucent lines, osteolysis & implant migration) 12 months post-surgery

Clinical Protocol

A Prospective, Multi-center, Study to Evaluate the Safety and Effectiveness of REAL INTELLIGENCE™ CORI™ in unicondylar knee arthroplasty (UKA) and total knee arthroplasty (TKA) procedures

Study Number: CORI.2019.07

Version: 6.0, 15/Jan/2024

Page: 8 of 122

- 2011 Knee Society Score (KSS) at baseline, 6 weeks, 6 and 12 month post-surgery
- Oxford Knee Score (OKS) at baseline, 6 weeks, 6 and 12 month post-surgery
- Forgotten Joint Score (FJS) at 6 weeks, 6 and 12 month post-surgery
- Five-level EuroQol five-dimensional (EQ-5D-5L) VAS and index scores at baseline, 6 weeks, 6 and 12 month post-surgery

Other exploratory endpoint(s):

- Leg alignment pre- and post-cementation
- Robotics System time as extracted from the Subject's CORI Robotics Case Report generated by the CORI Robotics Software.
- Cutting time of the robotic drill s extracted from the Subject's CORI Robotics Case Report, generated by the CORI Robotics Software.

Safety Data

- All adverse events (AEs) and complications occurring from the time of subject enrollment until study termination or study completion including intra-operative adverse events and complications.
- Device related re-intervention
- Device Deficiencies

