5.4 Claims

No claims to be confirmed by this investigation.

6.INVESTIGATIONAL PRODUCT(S)

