9.2.7 Robotic System Time & Cutting Time

The CORI Robotic System Time and the Cutting Time of the robotic drill shall be collected post-operatively.

The CORI Robotics Case Report, including case logs, will be extracted from the CORI system via USB and time data will be extracted for CORI Robotic System Time and the Cutting Time

In the case logs, the following time stamps will be recorded in the log file of the CORI Robotics Case Report:

1. State-Machine transition : [Adjust Camera] --> [Checkpoint Definition]
2. State-Machine transition : [Checkpoint Verification] --> [Remove Bone]
3. State-Machine transition : [Remove Bone] --> [Baseline Stress ROM Collection]

Robotics System Time

Robotics System starts with the checkpoint definition until the bone is removed. This is calculated by the time difference between #3 and #1.

Clinical Protocol

A Prospective, Multi-center, Study to Evaluate the Safety and Effectiveness of REAL INTELLIGENCE™ CORI™ in unicondylar knee arthroplasty (UKA) and total knee arthroplasty (TKA) procedures

Study Number: CORI.2019.07

Version: 6.0, 15/Jan/2024

Page: 54 of 122

Cutting Time

The Cutting Time of the robotic drill is the time from the start until the end of bone removal and is calculated by the time difference between #3 and #2.

The Robotics System time and the cutting time of the robotic drill will not be recorded in the eCRF as they will be extracted directly from the CORI Robotics Case Report.

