10.1 General

Smith Nephew's Global Biostatistics group will conduct the statistical analysis for this study. Unless otherwise stated, all significance tests and hypothesis testing will be two-sided, performed at the 5% significance level. Resulting p-values will be quoted and 95% two-sided confidence intervals

Clinical Protocol

A Prospective, Multi-center, Study to Evaluate the Safety and Effectiveness of REAL INTELLIGENCE™ CORI™ in unicondylar knee arthroplasty (UKA) and total knee arthroplasty (TKA) procedures

Study Number: CORI.2019.07

Version: 6.0, 15/Jan/2024

Page: 55 of 122

will be generated where appropriate. Where data summaries are specified, categorical and ordinal variables will be summarized with frequencies and percentages. Continuous variables will be summarized with the following summary statistics: the number of observations, mean, median, standard deviation, minimum and maximum values.

All statistical comparisons of data would describe the test statistic used as well as its distributional assumptions. For continuous variables, in an event of marked deviation from normality assumption, a commensurate non-parametric test would be used as an alternative thereby eliminating the possibility of violation of normality assumptions. All analyses will be performed using SAS version 9.3 (or a later version).

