10.4.3 Analysis of Other Endpoint(s)

The analyses for other endpoints (will be carried out separately in the CORI Robotics UKA and CORI Robotics TKA groups.

Leg alignment pre- and post-cementation

Leg alignment pre- and post-cementation will be summarized using descriptive summary characteristics for continuous variables.

Robotics System Time & Cutting Time

Robotic System and cutting times will be summarized using summary statistics for continuous variables. Standard Robotics System and cutting times will be obtained from literature and included in the SAP. The average operating (μ_{11}) and cutting times (μ_{21}) and their commensurate 95% CIs will be summarized compared to the obtained literature-specified (i.e. μ_{10} and μ_{20} respectively) using the t-test.

The following are the possible outcomes, where $i=1$ represents operating time and $i=2$ represents cutting time:

If the lower limit (LL) of the 95% CI for μ_{i1} is $> \mu_{i0}$, then it is concluded that μ_{i1} is significantly greater than μ_{i0} .

If the upper limit (UL) of the 95% CI for μ_{i1} is $> \mu_{i0}$, then it is concluded that μ_{i1} is significantly less than μ_{i0} .

If (LL of 95% CI for $\mu_{i1} \leq \mu_{i0} \leq$ UL for 95% CI of μ_{i1}), then it is concluded that μ_{i1} on-study is comparable to that specified in the literature (μ_{i0}).

All other endpoints will be summarized using the FAS analysis population.

Clinical Protocol

A Prospective, Multi-center, Study to Evaluate the Safety and Effectiveness of REAL INTELLIGENCE™ CORI™ in unicondylar knee arthroplasty (UKA) and total knee arthroplasty (TKA) procedures

Study Number: CORI.2019.07

Version: 6.0, 15/Jan/2024

Page: 59 of 122

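### The exploratory decision rule for Robotics System time and cutting time has its second inequality reversed, so its three outcomes overlap or leave a gap

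*Combined protocol and SAP*

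**What the plan says.** Section 10.4.3 (Analysis of Other Endpoint(s)) summarises Robotics System time and cutting time separately in the UKA and TKA groups. It compares each mean with a literature value by a t-test and a 95% CI. The benchmarks themselves are deferred: "Standard Robotics System and cutting times will be obtained from literature and included in the SAP".

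The section then lists the possible outcomes. With LL and UL for the 95% limits and μ0 for the benchmark, they are:

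1. LL > μ0: the study mean is significantly greater.
2. "If the upper limit (UL) of the 95% CI for" the study mean is > μ0: the study mean "is significantly less than" the benchmark.
3. LL ≤ μ0 ≤ UL: the mean "on-study is comparable to that specified in the literature".

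Section 10.1 sets the general standard: "all significance tests and hypothesis testing will be two-sided, performed at the 5% significance level". Section 9.2.7 defines the first quantity: "Robotics System starts with the checkpoint definition until the bone is removed". The outcome list in Section 10.4.3 calls it operating time.

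**The concern.** An upper limit above the benchmark is no evidence that the mean lies below it. Rules 1 and 3 together cover every interval except one whose upper limit is below the benchmark, so that is the only condition under which a conclusion of *less* makes sense. Rule 2 prints the opposite sign.

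Determining these two times is the whole of the study's other objective (Section 5.3), and the rule is applied four times: two times in each of two groups. Followed literally, it attaches incompatible conclusions to most results and none to the result most favourable to the device, a shorter time. An analyst would have to guess the intended sign after seeing the data, which is what the pre-specification in Section 8.4.4 is meant to prevent.

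Two wording points sit beside this. An interval that contains the benchmark is called comparable although no margin is given. And the label operating time could lead to a literature benchmark for the whole operation, which is not the interval defined in Section 9.2.7.

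**Working it through.** The plan gives no power, SD or benchmark for these endpoints, so it has no figure of its own to reproduce. The main check is logical; the probabilities only show how often each faulty outcome would arise.

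**Step 1. Every position of the interval**

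| 95% CI relative to μ0 | Rules met as printed | Rules met with rule 2 as UL < μ0 |
|---|---|---|
| Wholly above (LL > μ0) | 1 and 2: greater and less | 1: greater |
| Contains μ0, with UL > μ0 | 2 and 3: less and comparable | 3: comparable |
| UL exactly equal to μ0 | 3: comparable | 3: comparable |
| Wholly below (UL < μ0) | none | 2: less |

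The exact tie is the only printed case with one conclusion, and it has probability zero for a continuous time.

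**Step 2. Inputs for the probabilities**

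- Two-sided 95% t interval: Sections 10.1 and 10.4.3.
- n = 40 per group as enrolled, or 36 after the 10% attrition allowed for in Section 11. Times are captured at surgery, so 40 is the more relevant number.
- Assumed here: normal times, and true means 0, 0.2, 0.3 or 0.5 SD from the benchmark.

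**Step 3. Formula**

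Let T = (x̄ − μ0)/(s/√n) and c = t(0.975, n − 1), which is 2.023 for n = 40 and 2.030 for n = 36. Then LL > μ0 is the event T > c, UL > μ0 is the event T > −c, and UL < μ0 is the event T < −c. If the true mean is δ SD above the benchmark, T is noncentral t with n − 1 degrees of freedom and noncentrality δ√n.

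**Step 4. True mean equal to the benchmark (any n)**

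- Rule 2 as printed: P(T > −c) = 1 − 0.025 = 0.975.
- Rule 2 corrected: P(T < −c) = 0.025.
- Printed outcomes: less and comparable 0.950; greater and less 0.025; no conclusion 0.025.

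**Step 5. True mean different from the benchmark**

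| Shift (SD) | δ√n, n = 40 | Probability, n = 40 | δ√n, n = 36 | Probability, n = 36 |
|---|---|---|---|---|
| 0.2 | 0.2 × 6.325 = 1.265 | 0.234 | 0.2 × 6 = 1.2 | 0.214 |
| 0.3 | 0.3 × 6.325 = 1.897 | 0.457 (0.4565) | 0.3 × 6 = 1.8 | 0.417 |
| 0.5 | 0.5 × 6.325 = 3.162 | 0.869 | 0.5 × 6 = 3.0 | 0.831 |

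For a mean slower by the shift, each probability is the chance of greater and less together. For a mean faster by the same shift, it is by symmetry the chance of no conclusion.

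**Step 6. Simulation check**

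With 100,000 trials per scenario (shifts of 0, +0.5 and −0.5 SD; n = 36 and 40), the share of results meeting exactly one rule was 0.000 as printed and 1.000 with the sign corrected, in every scenario.

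**The case against.** The strongest reply is that this is an obvious typographical slip in an exploratory analysis. Rules 1 and 3 show what was meant. The means, intervals and p-values can still be reported, and no competent analyst would call a time shorter when its whole interval lies above the benchmark. Section 5.4 adds: "No claims to be confirmed by this investigation". All of this is fair, and it limits the damage to the verbal conclusions. It does not rescue the rule: saying the intent is clear concedes that the printed sign is wrong.

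Second, Section 10 describes itself as brief, with the SAP to be finalised before database lock. The supplied documents contain no separate SAP text, so the sign may already be right there. That stands as a limit on what can be said. Within the protocol, nothing restates the rule and neither amendment entry corrects it.

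Third, the point rests on one machine-transcribed symbol. The ≤ signs of rule 3 came through intact and nothing suggests a transcription fault, but the source page should be checked.

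Fourth, the probabilities in Step 5 are ordinary one-direction t-test power under assumed shifts, and Section 10.1 allows a non-parametric test if normality fails markedly. That is correct. The figures illustrate frequency only; the contradiction in Step 1 needs neither normality nor an assumed shift.

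**Conclusion.** The concern holds. As printed, rule 2 has the wrong sign, and the three outcomes are neither exclusive nor exhaustive: apart from a tie of probability zero, every result gets either two incompatible conclusions or none. With the true mean at the benchmark, the printed rule declares a shorter time 39 times as often as the corrected one (0.975/0.025).

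That ratio and the shift probabilities assume normal times and a t interval; the 0.2 to 0.5 SD shifts are illustrations, since the documents give no SD or benchmark. Confidence that the sign is wrong is high, subject to the source-page check. It should be fixed because it is a stated decision rule. Its reach is confined to the two exploratory time endpoints: the primary, secondary and safety analyses and the sample size are unaffected.

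**What to change.** Check the sign on the source page of Section 10.4.3. If it is as transcribed, change rule 2 so that the conclusion of a significantly shorter time requires the upper 95% limit to be below the benchmark, and carry the corrected rule into the SAP before database lock. The three outcomes are then exclusive and exhaustive and agree with the two-sided 5% level in Section 10.1.

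Make two wording changes at the same time. Report an interval containing the benchmark as showing no significant difference, rather than as comparable. Replace operating time with Robotics System time as defined in Section 9.2.7, so that the literature benchmark is chosen for the same interval.

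The cost is one sign and a few words, with no effect on data collection or sample size.

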11. SAMPLE SIZE JUSTIFICATION

Parratte et al.[53] looked at the effects of postoperative mechanical axis alignment on the survival of TKAs. They found that of the 398 TKAs reviewed in the paper there were 292 (73.4%) which post-operatively were defined as mechanically aligned (i.e. with a mechanical axis of $0^\circ \pm 3^\circ$).

This study is designed to demonstrate superiority in the proportion of TKAs post-operatively defined as mechanically aligned against the reference proportion of 73.4% from above.

Clinical Protocol

A Prospective, Multi-center, Study to Evaluate the Safety and Effectiveness of REAL INTELLIGENCE™ CORI™ in unicondylar knee arthroplasty (UKA) and total knee arthroplasty (TKA) procedures

Study Number: CORI.2019.07

Version: 6.0, 15/Jan/2024

Page: 60 of 122

The proportion of mechanically aligned TKAs using the NAVIO™ Surgical System from a recent analysis was estimated to be 92.1% [54]. If this assumption holds for this study, then the enrollment of 36 knees for each of the two planned study groups (i.e. the CORI Robotics UKA and CORI Robotics TKA) for a total of 72 knees will individually provide approximately 80% power to show that the lower limit of the two-sided 95% confidence interval for the proportion of mechanically aligned TKAs is greater than that obtained from literature. To account for up to a 10% attrition rate in knees enrolled, 40 knees in each group (80 knees combined, 40 UKA, 40 TKA) will be enrolled in the study.

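### Section 10.4.3 calls mean Robotics System and cutting times comparable to the literature whenever the 95% CI contains the literature value, with no margin; a minor flaw, because the endpoints are exploratory

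*Combined protocol and SAP*

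**What the plan says.** Section 10.4.3 covers Robotics System time (called operating time in its notation) and cutting time. "Standard Robotics System and cutting times will be obtained from literature and included in the SAP". The study means, with 95% CIs, are then compared with those values "using the t-test". Three outcomes follow:

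- The lower limit is above the literature value: the study mean is significantly greater.
- The upper limit is, as printed, also above the literature value: the study mean is significantly less. The inequality is reversed.
- The literature value lies between the two limits: the study mean "on-study is comparable to that specified in the literature".

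The analyses "will be carried out separately in the CORI Robotics UKA and CORI Robotics TKA groups". Section 10.1 sets the general standard: "all significance tests and hypothesis testing will be two-sided, performed at the 5% significance level". Section 10.4.3 gives no margin, SD or power for the times, and the literature times are the only item that it defers to the SAP.

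**The concern.** A two-sided 95% CI contains the literature value exactly when the two-sided 5% one-sample t-test is not significant. The third branch turns that non-rejection into a positive conclusion. Failing to detect a difference does not show that the difference is small, and the fewer or noisier the data, the easier the conclusion is to reach. The group size offers no protection, because Section 11 derives it from the leg-alignment proportion and not from the times.

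At stake is a statement about times that the data may not support. Determining these times is the only objective in Section 5.3, and Section 20.1 foresees registry posting and a manuscript, so the statement would probably be reported. Correcting the second inequality alone would leave this flaw in place.

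**Working it through.** The plan states no figure for this rule, so there is nothing to reproduce. The check asks how often the rule says comparable when a true difference exists.

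**Inputs**
- Rule: comparable if lower limit ≤ literature value ≤ upper limit (Section 10.4.3). The literature value is treated as known without error.
- Level: two-sided 5% (Section 10.1).
- n per group: 40 enrolled, and 36 after the 10% attrition allowance, since 36/(1 − 0.10) = 40. Section 11 bases its power statement on "the enrollment of 36 knees for each of the two planned study groups".
- Assumptions: times are normally distributed; the true difference *d* is expressed in SDs because neither an SD nor a literature value is given; the second branch is read with its inequality corrected. As printed, a CI that strictly contains the literature value meets both the second and the third branch.
- n = 20 is included only to show the effect of fewer usable case logs.

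**CI half-width**, in sample SDs: t(0.975, n − 1)/√n
- n = 36: 2.030/6 = 0.338
- n = 40: 2.023/6.325 = 0.320

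In the extreme case, where the lower limit just touches the literature value, comparable is still concluded with an upper limit 2 × 0.338 = 0.68 SD (n = 36) or 2 × 0.320 = 0.64 SD (n = 40) above it.

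**Probability of concluding comparable**: F(t; n − 1, δ) − F(−t; n − 1, δ), where F is the non-central t distribution function, t is the critical value above and δ = d√n. For d = 0.25, δ is 0.25 × 6 = 1.50 at n = 36 and 0.25 × 6.325 = 1.58 at n = 40. For d = 0.4, δ is 2.40 and 2.53.

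| True difference (SD, either direction) | n = 20 | n = 36 | n = 40 |
|---|---|---|---|
| 0 | 0.950 | 0.950 | 0.950 |
| 0.2 | 0.864 | 0.785 | 0.765 |
| 0.25 | not run | 0.692 | 0.662 |
| 0.3 | 0.753 | 0.583 | 0.543 |
| 0.4 | 0.603 | 0.354 | 0.306 |
| 0.5 | 0.435 | 0.169 | 0.131 |

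At every non-zero difference in the table the probability rises as n falls. At either planned size, a true difference of 0.3 SD is called comparable more often than not.

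**What a margin rule would deliver**: probability that the whole CI lies inside ± the margin when the true difference is zero (200,000 simulated samples per n; the margins are assumptions)

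| Margin (SD) | 95% CI, n = 36 | 95% CI, n = 40 | 90% CI, n = 36 | 90% CI, n = 40 |
|---|---|---|---|---|
| 0.3 | 2% | 4% | 12% | 18% |
| 0.4 | 30% | 39% | 52% | 60% |
| 0.5 | 66% | 74% | 81% | 86% |

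**The case against.** The strongest reply is that little hangs on this sentence. The synopsis labels the times exploratory, Section 5.3 sets out only to determine them, and Section 5.4 says that no claims are to be confirmed. The primary alignment test, the safety analyses and the sample size do not depend on the rule. The 95% CIs are to be reported anyway, so a reader would see the range behind any comparable label. Section 10 calls itself a brief description, and the SAP could add a margin. All of this stands and limits the importance. It does not repair the rule: the conclusion is written as automatic, and the protocol promises no margin.

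Three further points also stand. The times are captured at surgery (Sections 9.1.3 and 9.2.7), so n near 40, with the lower probabilities, is the more relevant case. The upper limits of 0.64 to 0.68 SD are the extreme and not a typical result. Without an SD, no one can say whether 0.25 or 0.4 SD matters in minutes.

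A reader might infer that the study could report that CORI adds no operating time. The documents do not support that. The benchmark is described as standard Robotics System and cutting times from the literature, no conventional-surgery benchmark is named, and Section 6.1.2 says that there is no comparator. A reader might also infer that the rule is tilted in the device's favour. It is symmetric: a truly shorter time would equally be labelled comparable.

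**Conclusion.** The point holds as a minor one. The third branch draws a conclusion of similarity that a non-significant test cannot support, and nothing else in the protocol qualifies it. Its size rests on assumed differences in SD units, normally distributed times, 36 to 40 analysable cases per group and a corrected second branch. The documents do not show that a difference missed in this way would be important in minutes, and they do not support any wider inference about the device's effect on operating time.

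**What to change.** Replace the third branch with: *the study does not show a difference from the literature value; the 95% CI gives the range of differences compatible with the data*. Correct the second inequality in the same edit, so that significantly less requires the upper limit to be below the literature value. This changes one sentence and one sign and needs no more patients. The downside is that the automatic comparable statement is lost.

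If the sponsor wants a comparability statement, allow it only when the whole CI lies within a justified margin in minutes, fixed in the SAP before the time data are analysed. Asking for the margin before the times are extracted would be impractical, because Section 9.1.3 has the case reports collected at each operation. This option costs more than a sentence. The margin needs a justification, and the SAP should state that power is limited: at n = 36 with a true difference of zero, the 95% CI falls within ±0.4 SD about 30% of the time and within ±0.5 SD about 66%.

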8.3.3 Other Endpoints

The following additional endpoints collected during surgery have been defined for this study:

- Leg alignment pre- and post-cementation
- Robotics System time as extracted from the Subject's CORI Robotics Case Report generated by the CORI Robotics Software.
- Cutting time of the robotic drill s extracted from the Subject's CORI Robotics Case Report, generated by the CORI Robotics Software.

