9. STUDY PROCEDURES

9.1 Visits and Examinations

9.1.1 Summary

For a summary of the required procedures by visit, refer to the Study Schematic Table 9-1:

Clinical Protocol

A Prospective, Multi-center, Study to Evaluate the Safety and Effectiveness of REAL INTELLIGENCE™ CORI™ in unicondylar knee arthroplasty (UKA) and total knee arthroplasty (TKA) procedures

Study Number: CORI.2019.07

Version: 6.0, 15/Jan/2024

Page: 43 of 122

Table 9-1: Study Procedures by Visit

Schedule of events	Pre-Operative Data -90 to 0 days	Operative Data & Discharge Day 0 (+ up to 9 days) ⁴	6 weeks 42 ± 14 days	6 months ⁵ 185 ± 14 days	12 months 365 ± 30 days
Informed Consent	X				
Inclusion/Exclusion	X				
Demographics/ Medical History	X				
Concomitant Medication Update		X	X	X	X
Operative Data Collection		X			
Knee Implant Disposition		X			
CORI Robotics Case Report (Robotic System time & cutting time)		X			
Discharge Data Collection		X			
Leg alignment Long leg X-ray AP	X	(X) ¹	X		(X) ²
Standard Lateral X-ray		(X) ¹	X		X
Standard A/P X-ray					X
KSS	X		X	X	X
OKS	X		X	X	X
FJS			X	X	X
EQ-5D-5L	X		X	X	X
Safety Assessment		X	X	X	X
End of Study/Exit			(X) ³	(X) ³	(X) ³

¹ Post-operative standing weight bearing long leg X-rays (A/P & L) may be taken at discharge if standard of care.

² Only if standing weight bearing long leg A/P X-ray is taken as a standard of care at 12 months.

³ Exit form to be completed at the point of withdrawal if the study is not completed.

⁴ If any Pre-Operative data is collected on the day of surgery, it must be completed prior to the surgery occurring.

⁵ The 6 month visit may be conducted remotely

Clinical Protocol

A Prospective, Multi-center, Study to Evaluate the Safety and Effectiveness of REAL INTELLIGENCE™ CORI™ in unicondylar knee arthroplasty (UKA) and total knee arthroplasty (TKA) procedures

Study Number: CORI.2019.07

Version: 6.0, 15/Jan/2024

Page: 44 of 122

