9.1.3 Operation Visit & Discharge (Day 0 up to Day 9)

If any Pre-Operative data is collected on the day of surgery, it must be completed prior to the surgery occurring.

1. Check if there is any change in eligibility of the subject since the pre-operative visit. If the subject is no longer eligible, document as screening failure.
2. Query subject regarding any changes in general health and the use of concomitant medications/therapies.
3. Collect data on the surgical plan: Target Leg alignment as entered into the CORI Robotics.
4. Perform surgery and collect intra-operative data on the appropriate eCRF. This includes but is not limited to the following information:

Clinical Protocol

A Prospective, Multi-center, Study to Evaluate the Safety and Effectiveness of REAL INTELLIGENCE™ CORI™ in unicondylar knee arthroplasty (UKA) and total knee arthroplasty (TKA) procedures

Study Number: CORI.2019.07

Version: 6.0, 15/Jan/2024

Page: 45 of 122

- Knee Implant Disposition (recording of tibial baseplate, insert and femoral component name, reference & lot/batch number)
- Surgical data (e.g. duration, blood loss, surgical approach)
- Collect pre- (with the trial implant in place) and post cementation alignment with the use of CORI Robotics.
- Collect the Subject's CORI Robotics Case Report, generated CORI Robotics Software (Robotics System time, cutting time)

5. Complete discharge eCRF.
6. If any adverse device effects or device deficiencies are observed or reported, they must be recorded as instructed in Section 12 - Adverse Events and Device Deficiencies.
7. Instruct the subject on proper postoperative care/procedures, including any contraindicated treatments/medication(s).
8. Instruct the subject returning to the site for the next follow up visit 6 weeks (42 ± 14 days) after the surgery date.

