10.2 Analysis Populations

The following are the analysis populations:

- Safety Population (SAF): This is defined as all subjects who were treated for a UKA or TKA with the use of the CORI Robotics and a Smith+Nephew Knee Implant System.
- Full analysis set population (FAS): The FAS is a subset of the subjects of the SAF population who have at least one post-operative assessment on any of the effectiveness endpoints or health-related quality of life (HRQoL) endpoints.
- Per-Protocol Population (PP): The PP population is a subset of subjects in the FAS population who do not have major protocol deviations and who satisfied all enrollment eligibility criteria. Major protocol deviations will include but not only restricted to subjects enrolled who do not satisfy the study entry eligibility criteria. All other criteria that will be categorized as major deviations will be formally classified on a case-by-case basis prior to the final study database lock.

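### Endpoints measured during surgery are analysed in a set that requires a later assessment; all treated subjects with operative data could be used instead (small, free improvement)

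*Combined protocol and SAP*

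**What the plan says.** Section 8.3.3 introduces three endpoints with the words "The following additional endpoints collected during surgery have been defined for this study": leg alignment before and after cementation, Robotics System time, and cutting time of the robotic drill. Section 9.1.3 places the alignment readings in the operation itself: "Collect pre- (with the trial implant in place) and post cementation alignment with the use of CORI Robotics". Section 9.2.7 derives both times from time stamps in the CORI case log.

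Section 10.4.3 assigns the analysis set for all three: "All other endpoints will be summarized using the FAS analysis population". It also compares the mean times with literature values by t-test and concludes greater, less or comparable from the 95% confidence interval.

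Section 10.2 defines the two relevant sets. For the SAF: "This is defined as all subjects who were treated for a UKA or TKA with the use of the CORI Robotics" (and a sponsor implant), with no follow-up condition. For the FAS: "The FAS is a subset of the subjects of the SAF population who have at least one post-operative assessment" on any effectiveness or quality-of-life endpoint. The SAF is used for the baseline summaries (10.3, alongside the FAS and PP sets) and for safety (10.5). No section exempts the operative endpoints from the FAS condition.

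**The concern.** An outcome fixed on Day 0 should not need a later event before it is counted. Under section 7.6 a subject is enrolled only once treated with the study product, so each enrolled subject can have these data at the end of the operation. Requiring a later assessment can remove valid observations for reasons unrelated to how they were measured. Section 7.8.4 allows data collected before withdrawal of consent to be used, so the restriction discards data that the protocol permits.

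What is at stake is modest. These are exploratory endpoints with no success criterion. The two times do feed a stated comparison with literature values, so the analysis set affects a reported conclusion as well as a descriptive table.

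**Working it through.** **Inputs**
- Enrolled per group: 40. Evaluable per group: 36. Attrition allowance: up to 10% (section 11).
- Reference proportion 73.4%, expected proportion 92.1%, about 80% power (section 11); two-sided 5% (section 10.1).
- Intervals for mean times: two-sided 95%, with a t-test (section 10.4.3).
- Number of treated subjects with no post-operative assessment at all: not stated. Call it k, and take 0 to 4 per group as an assumed range.
- SD of the times and of the alignment readings: not stated, so results are in SD units, with the same SD assumed in both sets.

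**Step 1. The plan's own figures.** The two-sided score approximation for one proportion gives

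n = [(1.96 × √(0.734 × 0.266) + 0.842 × √(0.921 × 0.079)) / (0.921 − 0.734)]² = 34.2, so 35, against the stated 36.

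Attrition: 36 / 0.90 = 40, exactly as stated. The allowance is therefore 40 − 36 = 4 subjects per group.

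**Step 2. Who is dropped.** The FAS asks for one assessment on any effectiveness or quality-of-life endpoint, with no time limit. The ways in are:
- a post-operative radiograph, which "may be taken at discharge if standard of care" (Table 9-1, footnote 1); section 9.2.2 accepts component alignment from discharge;
- the 6-week, 6-month or 12-month visit, where one questionnaire is enough;
- a full Exit Visit on early discontinuation, where possible (section 9.1.9).

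Only a treated subject with none of these is excluded. So k is at most 4 if attrition stays within the allowance, and reaches 4 only if all of that attrition lacks every assessment.

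**Step 3. Precision.** Half-width of the 95% interval for a mean, in SD units: t(0.975, n − 1) / √n.

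**Step 4. Shift in the mean.** With D = mean of excluded cases minus mean of retained cases, the all-treated mean equals the retained mean plus (k/40) × D. The FAS mean therefore differs from the all-treated mean by (k/40) × D.

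| k | n in FAS | Half-width (SD) | Wider than n = 40 | Shift in mean |
|---|---|---|---|---|
| 0 | 40 | 0.320 | – | 0 |
| 1 | 39 | 0.324 | 1.4% | 0.025 × D |
| 2 | 38 | 0.329 | 2.8% | 0.05 × D |
| 4 | 36 | 0.338 | 5.8% | 0.10 × D |

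For an assumed D of 0.5, 1 or 2 SD in size, the shift at k = 4 is 0.05, 0.10 or 0.20 SD. All of these are smaller than the half-width of 0.320 SD with every case included.

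**The case against.** **Entry to the FAS is easy.** This stands. A reader might infer that anyone who leaves before the 6-week visit loses operative data. The documents do not support that: a discharge radiograph or an exit visit qualifies, and someone who merely misses the 6-week visit qualifies through a later questionnaire. Those left out would be mainly subjects who withdraw consent or are lost before any assessment.

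**The 10% is the wrong rate.** This also stands. It is a sample-size allowance for the 6-week alignment endpoint. A subject can miss that radiograph and still belong to the FAS.

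**The times may themselves qualify.** Section 9.2.7 says: "The CORI Robotic System Time and the Cutting Time of the robotic drill shall be collected post-operatively". Section 10.4.3 also sits under the efficacy heading. If the case report counts as a post-operative assessment, any subject with a usable log is in the FAS and nothing is lost for the times. Section 8.3.3 points the other way, and the 9.2.7 wording fits retrieval of a log written during surgery. It speaks only of the two times, not of the cementation readings. It would also leave the FAS condition nearly empty, including for the primary endpoint. On this reading the proposed change is harmless.

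**One effectiveness set throughout is conventional, and the endpoints are exploratory.** True, and this is why the point is minor. Convention gives no reason to tie a Day 0 measurement to later attendance when a set of all treated subjects is already defined.

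**Conclusion.** The point holds as a small one. On the natural reading, section 10.4.3 makes inclusion of intra-operative data depend on follow-up, and no other section corrects this. The likely loss is 0 to 4 of 40 per group, with 4 an unlikely ceiling. At that ceiling the interval for a mean is 5.8% wider and the mean moves by 0.1 × D; if every treated subject has some later assessment, the effect is nil.

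A reader might infer that long or difficult operations are over-represented among early exits, so that reported times look too short and alignment too good. The documents do not support this. Section 7.8.2 lists adverse events among many permitted withdrawal reasons, but nothing links procedure length or alignment to leaving early. The size and sign of D are unknown, so no direction of bias can be claimed.

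**What to change.** Replace the last sentence of section 10.4.3 with: *Endpoints collected during surgery (Robotics System time, cutting time, leg alignment pre- and post-cementation) will be summarized using all SAF subjects with available operative data.* These are the only endpoints listed in section 8.3.3, so none is left without an analysis set.

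Carry the same sentence into the SAP, which section 10 says is to be finalised before database lock. The cost is one sentence: no new data, and no change to the primary or secondary analyses. Declaring instead that operative data qualify a subject for the FAS would also solve the problem, but it would alter the set used for the primary endpoint, so the SAF wording is cleaner.
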